Subjects in Cohort 5 will receive two courses of IP; the first course will be accompanied with PPI. During the second course, some subjects will receive a H2 blocker, and some subjects will not. Subjects will be followed from the day of the first dose of study drug (day 1) until 28 days after the first dose (day 29), and then from the first day of their second course (day 29) until the

28th day following the first dose of that course (day 57). Subjects in that cohort will consume the HMO concentrate twice per day for 14 consecutive days during both courses of IP and will be followed until the 28th day following the first day of the second course of the feeding protocol for a total of 57 days.

IP will be packaged so that consumption will be one container of each component per dose, to be mixed immediately prior to ingestion, except for Cohorts 1 and 2 where the IP will consist of only one container per dose.

The PBCLN-005 will be presented in frozen liquid form while the *B. infantis* will be presented in a foil package as a lyophilized powder to be mixed with thawed PBCLN-005 or an appropriate alternative diluent prior to ingestion.

Each bottle of HMO concentrate will be filled to deliver the required amount of HMO. The daily target doses of concentrated oligosaccharide to be evaluated in this study are 4.5g, 9g and 18g. The daily dose of *B. infantis* is $\geq 8 \times 10^7$ CFU in a foil pouch. The dosing cohort regime is outlined as follows.

1. Study subjects randomized to Cohort 1 will consume by mouth *B. infantis* once per day for 7 consecutive days. Subjects will mix *B. infantis* in an aqueous diluent supplied by the pharmacy
2. Study subjects randomized to Cohort 2 will consume by mouth the HMO investigational product (IP) twice per day for 14 consecutive days.
3. Study subjects randomized to Cohort 3 will consume by mouth HMO investigational product (IP) twice per day for 14 consecutive days. *B. infantis* will be taken once per day for 7 consecutive days. The subject will mix HMO and *B. infantis*. On days 8-14, only HMO product will be consumed (*B. infantis* will not be taken).
4. Study subjects randomized to Cohort 4 will consume by mouth HMO investigational product (IP) twice per day for 14 consecutive days. *B. infantis* will be taken once per day for 7 consecutive days. The subject will mix HMO and *B. infantis*. On days 8-14, only HMO product will be consumed (*B. infantis* will not be taken).

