5. Study subjects randomized to Cohort 5 will undergo two consecutive dosing courses. During the first dosing course, they will consume by mouth HMO investigational product

(IP) twice per day for 14 consecutive days. PPI and *B. infantis* will be taken once per day for 7 consecutive days. On dosing days 1-7 the first dose of HMO will be preceded by one hour and up to two hours by a single dose of PPI to protect the *B. infantis* from the acid milieu of the stomach. The subject will mix HMO and *B. infantis* and ingest at least one hour after taking the PPI. On days 8-14, only HMO product will be consumed (neither the PPI nor *B. infantis* will be taken). Cohort 5 will undergo a second dosing course from days 29-42. For all subjects, the HMO and *B. infantis* will be taken in the same manner as the first dosing course. Note: Prior to Protocol Revision 4, two subjects have already been dosed in Cohort 5. The first four of the remaining subjects yet to be enrolled in this cohort will take an H2 blocker in the same manner as the PPI in the first dosing course. The remaining four subjects enrolled into Cohort 5 will not take any PPI or H2 blocker during the second dosing course.

6. Study subjects randomized to Cohort 6 will consume by mouth HMO investigational product (IP) twice per day for 14 consecutive days and *B. infantis* will be taken once per day for 7 consecutive days. On dosing days 1-7 the subject will mix one dose of HMO and *B. infantis* ingest. On days 8-14, only HMO product will be consumed (the *B. infantis* will not be taken).

Table 1 Dosing cohorts

Cohort	Target HMO Amount (days 1-14)	PPI Cohort 5 Only (Course 1 = Days 1-7)	H2 Blocker Cohort 5 Only (Course 2 = Days 29 – 35)	B. infantis (days 1-7)
1	None	No	N/A	Yes, one sachet
2	18g	No	N/A	None
3	4.5g	No	N/A	Yes, one sachet
4	9g	No	N/A	Yes, one sachet
5 ^A	18g	Yes	Yes (4 subjects) No (4 subjects)	Yes, one sachet
6	18g	No	N/A	Yes, one sachet

^A This group will undergo two dosing courses. One from day 1-14 and one from day 29-42. Four of the subjects in the second course will be assigned a H2 blocker and four of the subjects will not take any PPI or H2 blocker.

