NOTE: Prior to Protocol Revision 4, two subjects were enrolled in Cohort 5 based on the original dosing scheme. Thus, two subjects have already been dosed in Cohort 5. The first four of the remaining subjects yet to be dosed in the Cohort 5 second dosing course will take a H2 blocker in the same manner as the PPI in the first dosing course. The remaining four subjects enrolled into Cohort 5 will not take any PPI or H2 blocker during the second dosing course.

As the maximum quantity of human milk oligosaccharides in this study has previously been given to healthy adult volunteers with good tolerance and no treatment emergent adverse events⁶, this study will not be conducted in the manner of a dose escalation safety study. That is, the randomization scheme will allow for the assignment of any given study subject to any of the six cohorts rather than to fill the cohorts sequentially.

Samples of blood, urine and stool from all subjects will be taken at screening (day 0) to determine subject eligibility and to establish baseline values. Urine will only be required at screening. Stool samples will also be required on days 1, 5, 8, 15, 22 and 29, where day 1 is the first day of the feeding protocol. Blood samples will also be drawn on days 1, 8, 15, and 29. For dose group 5 ONLY, stool samples will also be required on days 33, 36, 43, 50 and 57 and blood samples on days 36, 43 and 57. Details regarding type of stool sample and its processing is described in the accompanying Laboratory Manual.

The summary of all study events is presented in Table 2 at the end of this protocol.

Sample Size

Six groups of 10 subjects will be included in this study for a total sample size of 60. The sample size was not determined statistically, but rather represents a typical number for an exploratory study of healthy volunteers.

Study Duration

Six separate cohorts of both male and female study subjects will receive some form of the IP. All subjects in Cohorts 1-4 and 6 will be followed from the day of the first dose of IP (day 1) until 28 days (day 29) after the first dose. Subjects in Cohort 1 will consume *B. infantis* once per day for 7 days. Subjects in Cohort 2-4 and Cohort 6 will consume the IP twice per day for 14 consecutive days. Cohorts 1-4 and Cohort 6 will be followed until the 28th day (day 29) following the first day of the feeding protocol (day 1).

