Subjects in Cohort 5 will receive two courses of IP. They will be followed from the day of the first dose of study drug (day 1) until 28 days after the first dose (day 29), and then from the first day of their second course (day 29) until the 28th day following the first dose of that course (day 57). Subjects in that cohort will consume the HMO concentrate twice per day for 14 consecutive days during both courses of IP and will be followed until the 28th day following the first day of the second course of the feeding protocol for a total of 57 days.

Study Population

Each subject must meet all of the indicated inclusion criteria and none of the exclusion criteria noted below.

Inclusion Criteria

- Healthy adults between the ages of 18-44 years (subjects must be 18-44 at the time of consent)
- Willingness to complete study specific questionnaires
- Willingness to complete journal to record IP dosing times
- Willingness to complete all study procedures and clinic visits, and provide required samples
- Able to provide stool samples on specific study days

- Willingness to collect and process stool samples at home and transport stool samples to clinic
- Bristol Stool Score of 1 through 5 at time of screening and on day 1, subjects must verbally confirm that they did not have stool conforming to Bristol Stool Score 6 or 7 during the 7 days prior to dosing.
- Able to store up to 9 days of IP in refrigerator
- Sexually active females of child-bearing potential must agree to use highly effective methods of contraception during heterosexual intercourse throughout the study period and for three days following discontinuation of IP, whichever comes later. Examples of highly effective methods include the use of two forms of contraception with one being an effective barrier method (e.g., a condom and spermicide used together), or have a vasectomised partner. Abstinence is acceptable as a life-style choice. Female subjects who utilize hormonal contraceptives as one of their birth control methods must have used the same method for at least 3 months before study dosing
- Provides informed consent

Exclusion Criteria

- Women who are pregnant or breastfeeding, or intend to become pregnant during the course of this study
- Subjects with allergy to, or other reason for contraindication of the PPIs or H2 blocker* chosen for this study.

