4.3 RANDOMIZATION AND BLINDING

The study will not utilize randomization or blinding.

Statistical Analysis Plan**Prolacta Bioscience Protocol 20-CT-001****4.4 SCHEDULE OF EVENTS**

The tables below give the schedule of events for each cohort.

Schedule of Events Table
Cohort 1

Protocol Number 20-CT-001																		
Schedule of Events For Cohort 1 (Day 0 through Day 29)																		
Events	Cohort 1 Screening	Cohort 1 Dosing Days															Cohort 1 Washout	
	D0 (≤ 90 days prior to D1)	D1	D2	D3	D4	D5 (+1D)	D6	D7	D8 (+2D)	D9	D10	D11	D12	D13	D14	D15 (+2D)	D22 (+2D)	D29 (+2D)
Clinic visit	X	X							X							X		X
Final Visit																		X
Informed consent	X																	
Review IE Criteria	X	X																
Medical History	X																	
Physical Exam	X																	X
Demographics (age, gender, ethnicity and race)	X																	
Vital Signs (Temp, BP, pulse, RR)	X	X							X							X		X
Height, weight and BMI	X																	
Prior & Con Meds	X	X							X							X		X
AEs		X							X							X		X

Statistical Analysis Plan

Prolacta Bioscience Protocol 20-CT-001

Cohort 1 (Cont.)

Protocol Number 20-CT-001																			
Schedule of Events For Cohort 1 (Day 0 through Day 29)																			
Events	Cohort 1 Screening	Cohort 1 Dosing Days																Cohort 1 Washout	
	D0 (≤ 90 days prior to D1)	D1	D2	D3	D4	D5 (+1D)	D6	D7	D8 (+2D)	D9	D10	D11	D12	D13	D14	D15 (+2D)	D22 (+2D)	D29 (+2D)	
Randomization		X																	
Dispense IP: B. infantis (≥8x10 ⁷ cfu/d) and aqueous dilute		X																	
Dosing: B. infantis (≥8x10 ⁷ cfu/d)		X	X	X	X	X	X	X											
Assess IP and Stool compliance										X								X	
Stool Questionnaires		X	X	X	X	X	X	X	X	X	X	X	X	X	X	X	X	X	
Daily Dosing and Flavor Questionnaire		X	X	X	X	X	X	X											
Patient Phone Calls			X	X	X	X	X	X											

Statistical Analysis Plan

Prolacta Bioscience Protocol 20-CT-001

Cohort 1 (Cont.)

Protocol Number 20-CT-001																		
Schedule of Events For Cohort 1 (Day 0 through Day 29)																		
Events	Cohort 1 Screening	Cohort 1 Dosing Days															Cohort 1 Washout	
	D0 (≤ 90 days prior to D1)	D1	D2	D3	D4	D5 (+1D)	D6	D7	D8 (+2D)	D9	D10	D11	D12	D13	D14	D15 (+2D)	D22 (+2D)	D29 (+2D)
Urine Drug Screen Test	X																	
Urine Pregnancy Test (Females of child-bearing potential)	X																	
Hematology & Chemistry testing	X	X														X		X

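### Cohort 5: H2 blocker versus none (4 v 4) is allocated by order rather than at random, and the amended SAP should name Cohort 5 course 1 versus Cohort 6 as the PPI contrast

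*Combined protocol and SAP*

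**What the plan says.** The Hypothesis section of the protocol sets two questions: whether the suspected inhibitory effect of PPI is real, and whether it is absent with famotidine. It adds that the intended subjects of later studies all take acid blockers.

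**Sequence.** In Cohort 5, "the first course will be accompanied with PPI" (Methods). The second course starts on Day 29. Footnote A to Table 1 says "Four of the subjects in the second course will be assigned a H2 blocker" and four take neither drug.

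**Who gets which.** Methods, item 5, says "The first four of the remaining subjects yet to be enrolled in this cohort will take an H2 blocker". The note under Table 1 says "The first four of the remaining subjects yet to be dosed in the Cohort 5 second dosing course will take a H2 blocker". The first orders subjects by enrolment, the second by second-course dosing. Study Procedure and footnote 2 of the Cohort 5 second-course schedule repeat the enrolment version. The note adds that "two subjects were enrolled in Cohort 5 based on the original dosing scheme".

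**Contraindication.** The Exclusion Criteria list "Subjects with allergy to, or other reason for contraindication of the PPIs or H2 blocker". The attached note limits the H2 part to Cohort 5 subjects due to receive that drug, and allows a contraindicated subject to take the second course without a blocker. Footnote 1 of the second-course schedule adds a check before H2 dosing.

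**Allocation to cohorts.** Protocol Methods: "the randomization scheme will allow for the assignment of any given study subject to any of the six cohorts". SAP 4.3: "The study will not utilize randomization or blinding".

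**Day 29 stool.** Stool Samples gives a window of up to 2 days late. The second-course schedule starts dosing on D29 and prints no window. Study Procedure states sampling before dosing for Day 1 only.

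**Analysis.** Everything is descriptive. SAP 5 gives each cohort its own column. SAP 7.4 is a heading only, and SAP 2 defers endpoint detail to an amended SAP.

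**The concern.** H2 blocker versus none is a fair comparison in one respect: both groups have had the same PPI course and are compared in the same period. It fails in another, because the groups are formed by who came first. Anything that changes over recruitment is then shared out unequally. The documents give reasons why something might change: the HMO material comes from pooled donor milk, and the *B. infantis* content of a sachet is stated as a minimum, so delivered amounts could differ between lots. The contraindication route is a second non-random way into the no-blocker group.

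PPI versus no PPI has a different weakness if it is read within subjects. PPI always comes first and no subject has the reverse order, so the difference between courses mixes drug with period and with earlier exposure to HMO and *B. infantis*.

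A descriptive analysis is no protection, since bias distorts a displayed difference as much as a test. The answer is also meant to inform later studies.

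**Working it through.** **The plan's own counts.** 6 × 10 = 60 subjects. In Cohort 5, 2 + 4 + 4 = 10, and Table 1 places the last eight. No SD, effect size or alpha is stated, so everything below is in SD units and serves as illustration.

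**Bias from allocation by order.** Assumption: the outcome drifts linearly over the eight subjects by a total of D. Give subjects the positions 0 to 7, each divided by 7.

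- First four: mean (0+1+2+3)/4/7 = 1.5/7 = 0.214.
- Last four: mean (4+5+6+7)/4/7 = 5.5/7 = 0.786.
- Bias = 0.571 × D. For D = 0.5, 1 or 2 SD this is 0.29, 0.57 or 1.14 SD.

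**The alternatives, at D = 1 SD.**

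| Allocation | Mean bias | Root mean square | Largest |
|---|---|---|---|
| By order (as planned) | 0.571 | – | 0.571 |
| Simple random, all 70 splits | 0 | 0.247 | 0.571 |
| Blocks of two, 16 allocations | 0 | 0.071 | 0.143 |

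In the simple random row, 0.571 is reached only by the planned split and its mirror image. For blocks of two, each pair contributes ±1/7 and four pairs are averaged, so the root mean square is (1/7)/√4 = 0.071.

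**Precision.** 95% half-width = t(0.975, n1+n2−2) × √(1/n1 + 1/n2).

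| Comparison | n | Half-width (SD) |
|---|---|---|
| H2 v none, as planned | 4 v 4 | 1.73 |
| One contraindicated subject moved to none, H2 place not refilled | 3 v 5 | 1.79 |
| One contraindicated subject set apart | 4 v 3 | 1.96 |
| Cohort 5 course 1 v Cohort 6 | 10 v 10 | 0.94 |

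The last row takes all ten Cohort 5 subjects as having had PPI in course 1, as Methods says. In Table 1 both cohorts have the 18 g HMO target and one sachet of *B. infantis* on the same study days, and differ in PPI.

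**Carry-over and Day 29.** The last first-course *B. infantis* dose is on Day 7 and the last HMO dose on Day 14, so course 2 begins 29 − 7 = 22 and 29 − 14 = 15 days later. Persistence over that gap is possible but not shown. Methods requires a Day 22 stool from all subjects; even with the longest printed window (+2 days) it falls by Day 24 and so precedes course 2. For Day 29, if dosing began on D29 and the stool came separately on D31, 2 or 3 of the 7 second-course *B. infantis* doses would be due first. If the window moves the whole visit, the sample can still be pre-dose. The text does not say which applies.

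**The case against.** **No one plans course 1 versus course 2.** A reader might infer that the PPI question rests on that contrast. The documents do not say so. SAP 5 tabulates by cohort, so Cohort 5 and Cohort 6 already stand in separate columns of the same tables. This stands: the case is for naming the cleaner contrast, not for correcting a planned wrong one. The bare heading at SAP 7.4 is not a fault either, because SAP 2 defers the detail.

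**Day 29 is not a declared baseline.** A reader might infer that the second-course baseline is contaminated. Methods ties baseline values to screening, no text names Day 29 as a baseline, and course-2 product is dispensed at the D29 visit, so a sample handed in there would normally be pre-dose. Day 22 already offers a carry-over check. This too stands, and leaves only a point of clarification.

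**The drift is assumed.** Also true. At 1 SD of drift the bias of 0.57 SD is about a third of the 1.73 SD half-width (0.57/1.73 = 0.33), and 4 v 4 in a descriptive study supports little in either case. But the imprecision is unavoidable at this size, whereas the order bias can be removed on average for the price of a list.

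**Randomising late disturbs eligibility.** The H2 exclusion applies to subjects due to receive that drug. If allocation follows the second-course check, no one has that status at screening. This is a fair point, and the exclusion note has to be reconciled with the allocation step.

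**Conclusion.** The concern holds for the allocation of H2 blocker versus none. It is by order, the protocol gives two different orders, and contraindication adds a second non-random route. The bias is 0.57 times whatever total linear drift exists over the eight subjects. That multiplier rests on linearity, and the drift itself is unknown.

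For PPI, a display of course 1 against course 2 would be confounded with period and prior exposure. It would be wrong to conclude that the trial cannot address PPI at all: Cohort 5 course 1 versus Cohort 6 avoids both problems. Its freedom from selection bias depends on cohorts having been randomised, on which the protocol and SAP 4.3 disagree. Nor do the documents show that carry-over occurs.

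The Day 29 timing is a minor ambiguity. Overall this is an inexpensive change worth making to a question the protocol sets out to answer.

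**What to change.** 1. **Allocation.** Among Cohort 5 subjects not yet assigned and cleared at the second-course contraindication check, allocate H2 blocker or none at random in blocks of two. Bring Methods item 5, the note under Table 1, the exclusion note, Study Procedure and the schedule footnotes into line with this. Show contraindicated subjects, and the second-course data of the two subjects who entered before Revision 4, separately. If everyone is already assigned, state the order-based allocation as a limitation.
2. **Contrast.** In the amended SAP 7.4, name Cohort 5 course 1 versus Cohort 6 at matched days as the PPI contrast and label course 1 versus course 2 as confounded with period. Reconcile the protocol with SAP 4.3 on randomisation.
3. **Day 29.** State that the Cohort 5 Day 29 stool is collected before the first course-2 dose, reconcile the window in Stool Samples with the second-course schedule, and use the Day 22 and Day 29 qPCR results to show any carry-over.

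**Cost.** A short list, one line on sampling, and text in an amendment already planned. The second allocation in each pair is predictable, though by then subjects have completed course 1. Setting contraindicated subjects apart can widen the interval (1.96 SD at 4 v 3, against 1.79 SD at 3 v 5). Randomising leaves 4 v 4 at 1.73 SD. No extra subjects are needed.

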An unconcentrated, pasteurized form of HMO material containing a proportional amount of lactose has already been used in an NIH sponsored clinical trial in premature infants with no reported ill effects.^v Prolacta Bioscience has also completed a healthy volunteer study using the same HMO material as in this trial (with no addition of *B. infantis*) which showed good tolerability. No treatment emergent adverse effects were reported over the course of the trial.^{vi}

The *B. infantis* preparation being used in this trial is a dietary supplement commercially available in the United States and marketed for use in infants. *B. infantis* is characterized as “generally regarded as safe” (GRAS).⁸

Hypothesis

The primary goal of this study is to evaluate the synergy of PBCLN-005 in varying doses with a fixed dose of *B. infantis*, compared with either component of the IP given alone. Synergy is defined as the enhanced gastrointestinal colonization of *B. infantis* upon feeding with HMO feeding. Secondary endpoints will measure changes in the gut microbiome, fecal metabolome and the subject’s immune status as measured by systemic markers. We hypothesize that the combination will result in greater proliferation of *B. infantis* than was seen with the HMO concentrate alone.

Another objective is to understand the role of the low pH of the stomach in colonization of *B. infantis*. For most non-spore forming gut bacteria, the stomach is a barrier to colonization since acid exposure can reduce bacterial titer by 1,000- to 1,000,000-fold. While some subjects in the study will take a proton pump inhibitor (PPI; Zegerid), or a proton pump inhibitor (Zegerid) and

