histamine H2-receptor antagonist (H2 blocker: Pepcid) to transiently reduce the production of gastric acid prior to *B. infantis* ingestion, some study groups will ingest *B. infantis* without PPI pretreatment. It was initially hypothesized that PPI might be necessary to observe *B. infantis* colonization distal to the acid milieu of the stomach. Preliminary data from the first group of subjects tested suggest that omeprazole may be inhibitory to *B. infantis* colonization and that colonization occurs in the absence of gastric acid suppression. *In vitro* data suggest that the inhibitory effect is not seen with the histamine H2-receptor antagonist famotidine. Therefore, this has resulted in a change to this hypothesis. We now seek to determine if colonization occurs in the presence of an acidic milieu in the stomach, if the apparent inhibitory effect of PPI on colonization is real and if the prediction that the effect will not be seen with famotidine is correct because all target group subjects for future studies are on acid blockers.

We also hypothesize that ingestion of PBCLN-005 along with the *B. infantis* will result in a more marked change in immune markers than was seen in the previous study in healthy adults. We will, therefore, evaluate changes in circulating cytokine and growth factor levels following the ingestion of the IP compared to baseline levels and between dose groups.

Methods

We propose to conduct an unblinded six cohort multi-dose trial using 10 subjects per cohort for a total of 60 healthy adult volunteers ages 18-44 in order to evaluate the effects of the use of HMO Concentrate (PBCLN-005) and *B. infantis* on the human microbiome.

Six separate cohorts of both male and female study subjects will receive some form of the IP. All subjects in Cohort groups 1-4 and 6 will be followed from the day of the first dose of IP (day 1) until 28 days (day 29) after the first dose. Subjects in Cohort 1 will consume *B. infantis* once per day for 7 days. Subjects in Cohort 2-4 and Cohort 6 will consume the IP twice per day for 14 consecutive days. Cohorts 1-4 and Cohort 6 will be followed until the 28th day (day 29) following the first day of the feeding protocol (day 1).

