- Changes in viability of proteobacteria and *Enterococcus* will be determined by plating on selective media. These measurements will predictive for success in suppressing pathogenic bacterial relatives in future trials.
- Blood parameters, such as cytokine levels at study days -1, 8, 15 and 2 except for Cohort 5 who will also be evaluated on days 36, 43 and 57.
- Determination of the need for protection of *B. infantis* from stomach acid in order for engraftment of the organism into the gut microbiome to occur.

c) Adverse events will be summarized by severity and relationship to study product. All adverse events will be reported on the study case report form designated for this purpose. Any serious and unexpected adverse event determined by the investigator to be definitely or highly likely causally related with the consumption of IP should be reported immediately (but no later than within 24 hours) to the Sponsor's Medical Monitor.

d) Baseline measures as of study entry

e) IP Feeding Protocol

- f) The dose level of PBCLN-005 consumed will be recorded as well as consumption of *B. infantis*.
- g) Demographics; age, gender, ethnicity and race
- h) Stool changes in subject's stool per Bristol Stool Score
- i) IP taste/ flavor on dosing days using a visual acuity scale

Statistical evaluation

Since this is an initial study of the use of PBCLN-005 in combination with *B. infantis*, it is, by definition, hypothesis-generating. Therefore, all statistical analyses will be descriptive. The various indices reflecting the microbiome will be summarized with appropriate descriptive statistics at each day of collection and compared qualitatively across time and by dose. Other quantitative outcome data collected will be summarized by means/medians and standard deviations/inter-quartile ranges. Graphics such as box plots also will be presented. Safety data (tolerability and adverse events) will be presented in tables with proportions (per subject) by dose and overall.

Schedule of Events Tables**Schedule of Events Table**
Cohort 1

Protocol Number 20-CT-001																			
Schedule of Events For Cohort 1 (Day 0 through Day 29)																			
Events	Cohort 1 Screening	Cohort 1 Dosing Days																Cohort 1 Washout	
	D0 (≤ 90 days prior to D1)	D1	D2	D3	D4	D5 (+1D)	D6	D7	D8 (+2D)	D9	D10	D11	D12	D13	D14	D15 (+2D)	D22 (+2D)	D29 (+2D)	
Clinic visit	X	X							X								X	X	
Final Visit																		X	
Informed consent	X																		

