4 STUDY METHODS

4.1 STUDY DESIGN

The study is an unblinded six cohort multi-dose trial using 10 subjects per cohort for a total of 60 healthy adult volunteers ages 18-75 in order to evaluate the effects of the use of HMO Concentrate (PBCLN-005) and *B. infantis* on the human microbiome.

Six separate cohorts of both male and female study subjects will receive some form of the IP. In Cohort 1, the IP will consist of the standard dose of *B. infantis* alone. In cohort two, the IP will consist of only the PBCLN-005. In Cohort groups 3, 4, 5, and 6, the IP will consist of varying dose levels of PBCLN-005 together with *B. infantis*, with each cohort getting a single dose level of HMO. In Cohort groups 3, 4, 5, and 6, the IP will contain a standard dose of *B. infantis*.

Table 1 below summarizes the cohort dosing.

Table 1 Dosing cohorts

Cohort	Target HMO Amount (days 1-14)	PPI (days 1-7)	B. infantis (days 1-7)
1	None	Yes, 20 mg	Yes, one sachet
2	18g	Yes, 20 mg	None
3	4.5g	Yes, 20 mg	Yes, one sachet
4	9g	Yes, 20 mg	Yes, one sachet
5A	18g	Yes, 20 mg	Yes, one sachet
6	18g	No	Yes, one sachet

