5 SUMMARY OF STUDY DATA

All continuous variables will be summarized using the following descriptive statistics: n (non-missing sample size), mean, standard deviation, median, maximum and minimum. The frequency and percentages (based on the non-missing sample size) of observed levels will be reported for all categorical measures. In general, all data will be listed, sorted by cohort and subject, and when appropriate by visit within subjects. All summary tables will be structured with a column for each cohort.

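### No dose contrast is named for *B. infantis*, and protocol and SAP disagree on which 18 g combination cohort matches the other cohorts on PPI use

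*Combined protocol and SAP*

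**What the plan says.** The protocol's Hypothesis section sets the aim: "The primary goal of this study is to evaluate the synergy of PBCLN-005 in varying doses with a fixed dose of" the probiotic organism, *B. infantis*. Cohort 1 (*B. infantis* only) and Cohort 2 (HMO only) supply the comparators, since the combination is to be "compared with either component of the IP given alone". The Methods section adds: "The daily target doses of concentrated oligosaccharide to be evaluated in this study are 4.5g, 9g and 18g".

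On acid suppression, the Hypothesis section reports: "Preliminary data from the first group of subjects tested suggest that omeprazole may be inhibitory to" colonization by *B. infantis*. Protocol Table 1 limits PPI to one cohort; its column is headed "PPI Cohort 5 Only (Course 1 = Days 1-7". SAP 4.1 describes Cohorts 3 to 6 as combination groups, "with each cohort getting a single dose level of HMO", but its own Table 1 shows PPI in Cohorts 1 to 5 and none in Cohort 6. The SAP's section on the purpose of the analyses agrees with that table: most subjects take a PPI and one group does not.

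The comparison rule, in the protocol's Statistical evaluation, is that microbiome indices are "summarized with appropriate descriptive statistics at each day of collection and compared qualitatively across time and by dose". SAP 6 repeats the endpoint and adds no contrast, day or summary measure. SAP 7.4, on PPI, is a heading without text. SAP 5 fixes the layout: "All summary tables will be structured with a column for each cohort". SAP 2 says that this version concentrates on safety and that the primary and secondary analyses will be expanded in an amended SAP.

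**The concern.** A dose comparison needs one cohort to stand for 18 g, and two combination cohorts could. They differ in a factor that the protocol itself suspects of acting on the primary endpoint. The plan does not say which one to use, and the two documents point to different answers.

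An analyst who works from the SAP sees Cohorts 1, 3, 4 and 5 sharing PPI use and would reasonably build the dose-response from them. If subjects were treated as protocol Table 1 describes, that choice sets a PPI-treated 18 g group against PPI-free groups at 0, 4.5 and 9 g. A real dose response could then look flat or reversed. The design does contain a set of four cohorts alike in acid-blocker status, but neither document names it as the basis for the dose comparison.

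**Working it through.** **Plan's own figure.** 6 cohorts × 10 subjects = 60, which reproduces. The documents give no SD, expected change or PPI effect size, so all effect sizes below are assumptions.

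**Step 1. Allocation, side by side.**

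| Cohort | HMO | *B. infantis* | PPI, protocol Table 1 | PPI, SAP Table 1 |
|---|---|---|---|---|
| 1 | none | yes | no | yes |
| 2 | 18 g | no | no | yes |
| 3 | 4.5 g | yes | no | yes |
| 4 | 9 g | yes | no | yes |
| 5 | 18 g | yes | yes (course 1) | yes |
| 6 | 18 g | yes | no | no |

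The cohorts alike in PPI status at 0, 4.5, 9 and 18 g with *B. infantis* are 1, 3, 4 and 6 under the protocol, and 1, 3, 4 and 5 under the SAP.

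**Step 2. Effect of the choice if the protocol's allocation applies.** Assume mean log10 rises without PPI of 1.0, 1.5, 2.0 and 2.5 at 0, 4.5, 9 and 18 g, and a PPI loss of L = 1 log10. The 18 g point is then 2.5 from Cohort 6 or 2.5 − 1 = 1.5 from Cohort 5. The second value is below the 2.0 at 9 g.

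The fitted 0-to-18 g rise is 18 × Sxy / Sxx. The mean dose is 31.5/4 = 7.875, so the deviations are −7.875, −3.375, 1.125 and 10.125, and Sxx = 177.19.

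- Cohort 6 at 18 g: Sxy = −7.875 − 5.0625 + 2.25 + 25.3125 = 14.625. Rise = 18 × 14.625/177.19 = **1.49**.
- Cohort 5 at 18 g: Sxy = 14.625 − 10.125 × 1 = 4.5. Rise = 18 × 4.5/177.19 = **0.46**.
- Cohorts 5 and 6 pooled, weighted by subject (10/10/10/20; mean dose 9.9; 18 g mean 2.0): with weights 1, 1, 1, 2, Sxy = −9.9 − 8.1 − 1.8 + 32.4 = 12.6 and Sxx = 259.2. Rise = 18 × 12.6/259.2 = **0.875**.

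**Step 3. Range for L, with Cohort 5 at 18 g.** Rise = 18 × (14.625 − 10.125 L)/177.19.

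| L (log10) | 18 g point | 18 g minus Cohort 1 | Fitted rise |
|---|---|---|---|
| 0 | 2.5 | 1.5 | 1.49 |
| 0.5 | 2.0 | 1.0 | 0.97 |
| 1 | 1.5 | 0.5 | 0.46 |
| 2 | 0.5 | −0.5 | −0.57 |

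Under these means, 18 g falls below 9 g once L exceeds 0.5. The fitted trend changes sign at L = 14.625/10.125 = 1.44.

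**Step 4. The mirror case.** If SAP Table 1 describes what was given, and the same 1-log loss applies in Cohorts 1 to 5, their means at 0, 4.5, 9 and 18 g are 0, 0.5, 1.0 and 1.5, while Cohort 6 stays at 2.5. The 18 g minus Cohort 1 difference is 1.5 with Cohort 5 but 2.5 with Cohort 6. The cohort that is safe under one table is confounded under the other.

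**Step 5. Precision of a named difference.** For 10 against 10 with equal SD, the 95% half-width is 2.101 × √(2/10) = 0.94 SD. An interval would show this uncertainty; a qualitative comparison would not.

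**The case against.** The strongest reply is that the gap is announced. SAP 2 says that the primary analysis will be expanded later, and the study is descriptive and hypothesis-generating. That stands, and it makes the amended SAP the right place for the fix. It does not settle the 18 g question, because an amendment that starts from SAP Table 1 would start from an allocation that the protocol contradicts.

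A second reply is that by dose simply means by cohort. The protocol calls Cohort 5 a dose group, and SAP tables have one column per cohort. This largely stands. A reader might infer that Cohorts 5 and 6, or even Cohort 2, will be merged under an 18 g label, but the documents do not support that. Cohort 2 gets no *B. infantis* and is a stated comparator. Separate columns still do not say which one is the 18 g point.

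Third, Cohort 5 already has its own purpose: acid protection is a separate objective and a secondary endpoint. That is fair, but no text keeps Cohort 5 out of the dose comparison.

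Fourth, the quoted rule speaks of microbiome indices and does not name the primary endpoint. However, the protocol places *B. infantis* qPCR under Microbiome Samples, and no other text supplies a primary contrast.

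**Conclusion.** The concern holds in this form: no dose contrast is named, and the documents disagree on which 18 g combination cohort is comparable with Cohorts 1, 3 and 4. If the protocol's allocation applies, using Cohort 5 lowers the 18 g point by the whole PPI effect. In the illustration the fitted rise goes from 1.49 to 0.46 log10 for a 1-log loss, and becomes negative above 1.44 log. These sizes rest on assumed means, an assumed PPI loss and a linear summary. That PPI inhibits colonization is only a suspicion drawn from preliminary data.

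Two stronger readings should be resisted. A reader might infer that the PPI-treated 18 g group could produce a false synergy claim. Under the protocol's allocation the suspected bias runs the other way, masking or reversing a dose response. A reader might also infer an inflated type I error. The plan sets no alpha and proposes no tests, so there is no nominal rate to exceed. The weakness is an undefined comparison that can be built on the wrong cohort.

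**What to change.** First, reconcile protocol Table 1 with SAP Table 1 and the SAP's purpose section on acid-blocker allocation. Then put the following in SAP 6 of the amended SAP, with a matching sentence in the protocol's Statistical evaluation. Do this before further *B. infantis* results are examined, since the study is unblinded and early results have already changed one hypothesis.

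- The dose comparison of log10 *B. infantis* change uses only cohorts with the same acid-blocker status as Cohort 1. Under protocol Table 1 these are Cohorts 1, 3, 4 and 6, with Cohort 6 as the 18 g point.
- Each dose-minus-Cohort 1 difference is reported with a 95% interval at one named day, chosen from the post-baseline stool days (5, 8, 15, 22, 29). All the differences are shown, with a dose trend as a descriptive summary.
- Cohort 5 is used only for the acid-blocker question, against Cohort 6.
- Cohort 2 is used only as the HMO-alone comparator for the 18 g combination.

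The study stays descriptive. The cost is a few sentences, with no added subjects, samples or visits. One small drawback is that a linear trend describes a plateau less well than the separate differences, which remain on display.
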